2.3 Study Drug (NITRITE)

The study drugs are oral formulation of sodium nitrite and matching placebo. Sodium nitrite is available in dose strengths of 20 mg and 40 mg. Sodium nitrite of both dose strengths and matching placebo will be supplied as capsules for oral administration. All capsule formulations will be identical in appearance (size, shape, color) and smell. The packaging and labeling will be designed to maintain blinding to the Investigator's team and to subjects.

2.3.1 Study Drug Preparation and Dispensing

The NO₂ and placebo capsules will be prepared at and obtained from Triangle Compounding Pharmacy, Inc., Cary, NC and the University of Pittsburgh Medical Center Investigational Drug Pharmacy Service (UPMC-IDS) will be utilized for dispensing of the study drug/placebo. The labeling and packaging will be conducted according to Good Clinical Practice and regulatory requirements. The study drug is administered only to subjects enrolled in the study and in accordance with the protocol.

Drug will be dispensed in four 7-day pill containers, with compartments for each dose, each labeled with subject name and directions for taking. Subjects will be given an additional capsule supply in a pill bottle as needed to maintain an adequate supply for the post-visit follow-up testing period.

2.3.2 Drug Administration

Standard ¹⁴N Sodium NO₂ or placebo will be supplied as one capsule, three times daily oral administration at the dose strength of 20 or 40 mg (per subject as described in Study Design section), in four 7-day pillboxes for the first 28 days on drug, and then additional supplied for subjects to refill boxes dependent on their individual visit schedule.

Hemodynamic effects of NO₂ in the HFpEF subjects included significant decreases in RA, RV systolic and diastolic, PA systolic/diastolic/mean, and PCWP. PCWP and MPAP decreased by 7.8 and 7.0 mm Hg, respectively (baseline median values 18 and 34 mm Hg, respectively). MetHb levels increased modestly but did not meet stopping criteria of the study. [name] presented his work at the American Thoracic Society Meeting in March, 2016. Overall, the data demonstrate feasibility and safety of aerosolized NO₂ in HFpEF, and in many respects corroborate the recently published analysis by Borlaug in a study of HFpEF patients aged 69 ±6 years that showed infused NO₂ benefits to acutely improve right heart hemodynamics during exercise¹. None of Borlaug's patients experienced hypotension or other adverse events. NO₂ levels were undetectable at baseline, but then increased to 8.39 ±1.88 μM. PCWP was substantially improved by NO₂ compared with placebo (p<0.0003). Likewise, cardiac output reserve improved with exercise (p<0.002) and an increase in cardiac output relative to O₂ consumption was normalized. NO₂ also improved pulmonary artery pressure flow relationships in HFpEF and increased left ventricular stroke work with exercise versus placebo, indicating an improvement in ventricular performance with stress.

As described in Section 1.4 Significance, the PI, [name], has an ongoing pilot study of oral NO₂ 40 mg tid with healthy controls, HFpEF and HFrEF subjects. Ten control subjects have completed the pilot without any significant product related adverse events. Mild and transient symptoms consistent with what other investigators have observed have been present in some of the other subjects.

Experience thus far in the pilot with heart failure subjects has suggested a tendency for a vasoactive response to nitrite not seen in the controls. Subjects with both HFrEF and HFpEF enrolled thus far have all required dose reductions to 20 mg tid to prevent hypotension. Thus we have adopted the stratified dosing as described for this protocol.

At this visit, methemoglobin will be assessed. If greater than 5%, the PI will be unblinded to drug or placebo assignment. If subjects are on nitrite, subjects will be asked to repeat drug dosing of 20 mg sodium nitrite with follow up methemoglobin and hemodynamic monitoring. A study physician or PI will evaluate data and make a determination regarding discharge on 20 mg tid. If discharged on 20 mg tid, subjects will be contacted via phone for the next 2 days for symptom re-assessment. If symptoms remain resolved, subjects will continue on 20 mg tid. If symptoms persist, subjects will be requested to come in for repeat methemoglobin testing after 3 days. If level persists above 5% on lower dose, participation in the study for the subject will be discontinued.

Hypotension and related symptoms.

In CTRC

If this occurs while in the CTRC, care will be administered, including fluids and monitoring, to ensure that the problem resolves and patient is stable. The physician investigator will factor relevant subject symptoms and hemodynamics and then decide whether unblinding is indicated and if it is appropriate for the subject to proceed with study participation prior to discharge from CTRC. This will include what dose is appropriate and drug dispensing. The same process will be applied to subjects who are initially initiated on 20 mg; however, in these subjects there is relatively greater consideration of withdrawal as no lower dosing options are available. The PI may indicate the need for a repeat pK with 20 mg dose in subjects who started on 40 mg study drug/placebo.

As outpatient:

If subjects experience lightheadedness or dizziness after visit 4 while they are on the study drug/placebo, we request that they call the study coordinator who will inventory their symptoms, compare to baseline levels (measured at pK), and discuss need for interim visit with study physician. If a visit is indicated, subjects will be asked to repeat drug dosing of 20 mg with follow up methemoglobin and BP pressure monitoring. A study physician will factor relevant subject symptoms and hemodynamics and will confirm a management plan including the:

- need for unblinding,
- possibility if subject was on sodium nitrite to lower dose to 20 mg tid or
- need to discontinue and drop from the trial.

If subjects proceed on lower dose they will be reassessed via phone each day for the next 2 days thereafter to ensure that the patient is stable on the new dose. If stable, subjects will continue with the half dose. However if there are continued symptoms on lower doses, the physician investigator will reevaluate the patient's suitability for continued participation based on symptoms and/or hemodynamics.

If subjects who were initiated on the 20 mg dose at Visit 4 report symptoms as described above, they will be asked to complete an interim visit, methemoglobin and BP pressure assessment; the physician may have to withdraw the subject since a dose lower than 20 mg tid is not an option.

Other symptom

The PI, via subject phone call monitoring, AE reports or at follow-up visits, will evaluate any other clinical presentation, sign or symptom in subjects which may warrant consideration of dose reduction. The procedure described for high methemoglobin or hypotension will be followed.

2.3.4. Treatment Period

Subjects will undergo study treatment duration of 4 weeks plus up to approximately 3 weeks of sodium NO₂ or placebo three times daily. Three additional weeks are included to allow continuation of the study drug/placebo through the final outcome collection series of visits. This is considered appropriate to study benefits of oral NO₂ therapy to improve physical function in patients with HFpEF.

Randomization and Blinding

We will use the high quality pseudo-random deviate generator in SAS® (SAS Institute, Inc., Cary, North Carolina) to randomize participants to NO₂ or placebo in 1:1 ratio with a random block size. Block sizes will be revealed to the rest of the study team at the conclusion of the study to prevent educated guessing. Randomization will be stratified by the initial dose (20/40 mg) depending on whether age ≥80 or age 70-80 and hypotension risk to the extent possible within the small sample size. Study statistician will create schedules which pairwise link the randomization sequence number, participant identifier and treatment arm, and call in all prescriptions thereafter by the randomization sequence number. The independent research pharmacist at the institutional Investigational Drug Service will package all drugs/placebos to be similar in physical appearance. We have successfully employed the same process in other recently completed trials¹⁰⁵. Therefore, all participants and study personnel involved in assessments will be blind to treatment assignment.

2.3.5 Breaking the Blind

Should the PI (or designated physician investigator) suspect that an adverse event (namely, methemoglobinemia, see Section 6.4.7) is related to the investigational product, he/she will contact one of three sources who will have access to the code:

1. the UPMC IDS
2. [name], Biostatistician-Investigator
3. [name], MSN, RN, CCRC, Director of Regulatory Affairs, Translational Research
Division of Pulmonary, Allergy, and Critical Care Medicine, Heart, Lung and Blood
Vascular Medicine Institute

They will be able to break the blind for that subject. An *emergency* unblinding/treatment would only be anticipated in the case of accidental overdose. In this protocol, signs and symptoms of methemoglobinemia are being monitored such that intervention would likely take place before reaching an emergent level if taken as prescribed. However, the PI and Coordinator will maintain quick access numbers to unblind quickly, if needed. Other signs and symptoms such as lightheadedness will be evaluated by the PI for determination if unblinding is indicated.

2.3.6. Medication Compliance

At Visit 4, subjects will self-administer their first dose of study medication under the supervision of the physician investigator or RN in the outpatient CTRC (Clinical Translational Research

Center) following completion of all baseline clinic assessments. After the pK (and subject is stable after first dose), subjects will be dispensed their study medication for home use, in, 4 prefilled seven-day labelled pill boxes to help with compliance and to help reduce burden or confusion. Pill counts will not be used during the first 28 days (phone call monitoring period) as having subjects remove the pills from the pill boxes to count would defeat the purpose of the pillboxes. On the weekly phone calls, the study coordinator will review the daily diary card (study drug/placebo and symptoms), inquire about missed doses and confirm empty pill boxes each week. Subjects will return empty pill boxes when they return for Visit 5, withholding those as needed for drug dosing during the final weeks. Medication compliance will be reviewed. Subjects will return any remaining capsules at their Visit 7 for final accountability. In the event that the compliance rate is <80% at any time reported by the subject, subjects will be re-educated on medication compliance. If medication compliance repeatedly falls outside of the acceptable range, the study investigators will discuss subject eligibility for continued participation in the study. Compliance during [name] pilot study has been excellent with no subject approaching the 80% level of concern.

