2. We hypothesize that decreased fatigability indices will correspond to increased daily activity as measured by actigraphy.
3. We hypothesize that the primary mechanism by which NO₂ decreases fatigability is improved bioenergetics as

measured by in vivo ^{31}P MRS and in vitro mitochondrial respiration and ATP generation.

4. We hypothesize that among HFpEF patients with pulmonary hypertension, NO_2 additionally mitigates fatigability by reducing pulmonary pressures and improving right ventricular-pulmonary artery coupling.

Study Design:

This is a prospective, randomized, double blind controlled trial of oral sodium nitrite vs. placebo in adults ($n=18$), ≥ 70 years of age with HFpEF.

Subjects who meet the Inclusion Criteria and none of the Exclusion Criteria will receive oral sodium nitrite or placebo for 4 weeks. We will stratify dosing as below:

Drug:

a. oral formulation of sodium nitrite 40 mg/placebo three times daily (tid), once in the morning and again in the early afternoon and again in the evening, approximately 6 hours apart in subjects age 70 to <80 years with low risk for hypotension

b. oral formulation of sodium nitrite 20 mg/placebo three times daily (tid), once in the morning and again in the early afternoon and again in the evening, approximately 6 hours apart in subjects ≥ 80 years of age, or subjects age 70 to <80 years with risk factors for hypotension

Subjects will be evaluated as outpatients with the first dose of study drug/placebo. Blood pressure (BP), heart rate (HR), respiratory rate (RR), oxygen saturation (SpO_2), methemoglobin % (MetHb) and plasma NO_2 will be measured at baseline and during the first two hours after dosing. Frequent safety monitoring will occur during the time subjects are on drug as well as after completion of the post drug assessments, by phone and in clinic to assess adverse events (AE), interval histories, and medication compliance and to monitor NO_2 and methemoglobin levels.

Study Aims

Aim 1: To complete a randomized, placebo-controlled trial in HFpEF patients aged ≥ 70 years to assess benefits of 1 month of NO_2 vs. placebo therapy to reduce perceived and performance fatigability and to improve aerobic functional capacity.

Aim 2: To delineate factors which underlie fatigability and the utility of NO_2 to modify them.

Planned Sample Size:

18 subjects: 9 sodium nitrite and 9 placebo

- Duration of Treatment:** 4 weeks plus range 2-3 weeks for post drug outcome assessments

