2.5 STATISTICAL ANALYSIS

2.5.1 Sample Size Determination

Formal sample size justifications based on statistical power for detecting significant differences at a strict 0.05 level are not applicable for a pilot study such as ours. We will use the descriptive statistics obtained herein for formal sample size and power computations in planning the larger subsequent trial to obtain more definitive findings. We will base our sample size on preliminary data from the present project, published statistical methods for sample size and power for approaches as similar as possible to the proposed analyses, and commercially available specialized software (PASS 2012[®]; Number Cruncher Statistical Systems, LLC, Kaysville, Utah) in planning the future trial to be proposed under the R01 mechanism.

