2.5.2 Study Conduct Analysis

We will clearly document participant flow from the number contacted to numbers screened, randomized and completed using a CONSORT diagram, with numbers and reasons for any exclusions, withdrawals, missed assessments and terminations at each stage. We will describe adherence to NO₂ therapy as measured by queries to subjects, self-report of empty compartments on weekly phone calls and pill counts at the post visits using summary statistics as well as any post-randomization adjustments. Insights gleaned from study conduct analyses will be used to adjust protocol in the subsequent larger trial to increase its feasibility.

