2.5.3 Efficacy Analysis

Overview-We will use SAS[®] version 9.3 (SAS Institute, Inc., Cary, North Carolina) for all analyses. The main focus of the analyses of the present pilot study will be to establish feasibility and obtain preliminary findings, and descriptive statistics needed for formal sample size and power computations for a subsequent larger randomized trial to be proposed under the R01 mechanism to obtain more definitive conclusions. Therefore, we will pay greater attention to magnitudes of effects rather than statistical significance alone, and similar to published pilot studies in other settings, also employ graphical methods such as needle plots that focus on change at the individual level rather than on average^{87, 88}. First, we evaluate the distributional characteristics of the data set, the prevalence of missing values and general data quality using appropriate descriptive statistics and graphical summarizations for all variables for each arm for each time point, as well as baseline to follow-up change scores. Second, the baseline measures and participant characteristics will be compared between the two arms using differences in magnitudes of the descriptive statistics, and independent samples *t*-, Wilcoxon rank sum, Kruskal-Wallis, chi-square or Fisher's exact tests, as appropriate. Any variables found to be meaningfully different will be noted when interpreting the findings. Third, main analyses below will be performed.

Aim 1-We will conduct Aim 1 analysis on an intention-to-treat basis. We will fit a series of linear mixed models using the SAS[®] MIXED procedure with baseline to follow-up change in primary outcome RPE, secondary outcome peak VO₂, and each of the other secondary outcomes as the

dependent variable; and treatment (NO₂/placebo), follow-up time (4 weeks) and their interaction as main factors of interest; baseline value of the dependent variable as the sole and a catch-all covariate; and a subject random effect to account for multiple follow-up measurements from each participant. We will construct appropriate means contrasts to compare the treatment groups at each of the follow-up time points. The magnitudes of the estimated means contrasts and graphical displays of individual change will be considered to support Aim 1 hypotheses rather than and in addition to statistical significance at the 0.05 level.

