6.4.7. Withdrawal of Subjects and Stopping Criteria

Withdrawal of Subjects due to Adverse Events:

As described in Section 2.3.3. Dose Selection, sub-section Dose Reduction, we propose to discontinue participation for any subject who experiences any of the following:

- a. Continued MetHB level >5% or continued lightheadedness and/or dizziness after protocol described in Section 2.3.3 for dose reduction is followed.

Other symptoms
- b. The PI, via subject phone call monitoring, AE reports or at follow-up visits, will evaluate any other clinical presentation, sign or symptom in subjects which may warrant consideration of interim visit and dose reduction. The procedure described in Section 2.3.3. Dose Selection, sub-section Dose Reduction (regarding drug discontinuation and determination or need to withdraw the subject) will be followed.

Other Reasons for Withdrawal

Medication compliance

- c. In the event that the medication compliance rate is <80%, subjects will be re-educated on medication compliance. If medication compliance repeatedly falls outside of the

acceptable range, the study investigators will discuss subject eligibility for continued participation in the study.

- d. Participants who complete the first biopsy and then state (prior to being given drug) that they will not complete a second biopsy at Visit 7 will be withdrawn from the study. Alternatively, patients who refuse the 2nd biopsy after they have completed the 4 weeks of NO₂/placebo therapy will still complete the other post drug assessments. If other unique subject situations arise, they will be evaluated by the PI and a decision will be made with regard to completing the other post assessments or not (e.g., completion of 2 weeks on drug, and then refusal to complete biopsy.)
- e. The PI will evaluate any other clinical presentation, sign, symptom or behavior in subjects which may warrant consideration of withdrawal.

Discontinuation of the Clinical Trial

Stopping Rule:

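### Repeated low compliance or mid-treatment refusal of the second biopsy can cost Aim 1 outcomes that could still be measured at Visit 5, which undermines the intention-to-treat analysis

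*Combined protocol and SAP*

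**What the plan says.** **Compliance.** Section 2.3.6 sets a first step: "In the event that the compliance rate is <80% at any time reported by the subject, subjects will be re-educated on medication compliance". The second step is: "If medication compliance repeatedly falls outside of the acceptable range, the study investigators will discuss subject eligibility for continued participation in the study". What is put in question is participation in the study, not only continued dosing. Section 6.4.7(c) repeats the rule among the non-safety reasons for withdrawal.

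**Second biopsy.** The Visit 4 biopsy text in section 2.2 and section 6.4.7(d) distinguish three times of refusal:
- Before any drug is given: the participant is withdrawn.
- After the 4 weeks of therapy: the other post assessments are still done.
- In between, with 2 weeks on drug as the example: the PI evaluates the case and "a decision will be made with regard to completing the other post assessments or not".

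**Analysis.** Section 2.5.3 states: "We will conduct Aim 1 analysis on an intention-to-treat basis". It does not define the analysis set. Section 2.5.5 plans multiple imputation with five data sets, but names no imputation variables, missingness mechanism or sensitivity analysis. Section 2.5.2 plans adherence summaries and a CONSORT diagram, and adds: "Insights gleaned from study conduct analyses will be used to adjust protocol in the subsequent larger trial to increase its feasibility". It does not say how withdrawn participants enter the adherence summary.

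**The concern.** An intention-to-treat estimate needs outcomes sought from everyone randomised, whatever their adherence. Here poor adherence, or declining a procedure that the primary outcome does not use, can end outcome collection.

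The loss may be related to arm. Sections 1.4 and 2.3.3 report that all heart failure participants enrolled so far in the earlier pilot needed a dose reduction to prevent hypotension, and section 6.1.1 lists hypotension as frequent in heart failure at higher nitrite doses. Missed doses or reluctance to continue could therefore reflect tolerability. The PI who decides on the post assessments may also know an individual's assignment after unblinding under sections 2.3.3 or 2.3.5. That route is narrow, since it needs two uncommon events in one participant.

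At stake are the size of the Aim 1 effect and the adherence figures carried into the next trial. Section 2.5.1 says: "Formal sample size justifications based on statistical power for detecting significant differences at a strict 0.05 level are not applicable for a pilot study". Section 2.5.3 gives weight to effect magnitudes rather than, and "in addition to statistical significance at the 0.05 level". A shift in magnitude therefore bears directly on what the pilot hands on.

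**Working it through.** The plan states no figure to reproduce: the sample size ("18 subjects: 9 sodium nitrite and 9 placebo") comes without a formula. The check is a comparison of the provisions, followed by an illustration of size.

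**Provisions side by side**
1. RPE after the steady-state walk and peak VO2 from the treadmill test are collected at Visit 5, 28 ± 3 days after Visit 4. The second biopsy is at Visit 7. Neither Aim 1 measure needs the biopsy or a given level of adherence.
2. The protocol already accepts outcome data without a second biopsy when refusal follows the 4 weeks of therapy. Skipping Visit 5 after an earlier refusal gains nothing for Aim 1.
3. No section separates stopping drug from leaving follow-up, and none asks for outcome visits after withdrawal. Section 6.4.2 follows participants who leave because of a serious adverse event until that event is settled. Section 7.2 pays withdrawn participants for visits already completed.

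**Effect estimate (illustration)**

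Assume k of the 9 nitrite participants are lost, the retained ones have mean change m, and the lost ones would have had mean r.
- All-randomised mean = [(9 − k)m + k·r]/9.
- Retained mean minus all-randomised mean = k(m − r)/9, so the sign depends on whether the lost participants respond less or more than the rest.
- With r = 0, the all-randomised effect is (9 − k)/9 of m: 8/9 = 89%, 7/9 = 78%, 6/9 = 67% for k = 1, 2, 3. Dropping the lost participants overstates it by 9/(9 − k): 1.13, 1.29, 1.50.
- Example with m = −2.0 and k = 1: (8 × −2.0 + 0)/9 = −1.78, against −2.00 among the retained, a shift of 0.22 points on the 6–20 scale.
- Imputing the lost participants from retained participants in the same arm gives the same factors in expectation if nothing in the imputation model predicts their poorer response.

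**Precision**

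SE ratio when k are lost from one arm without imputation = √(1/9 + 1/(9 − k)) / √(2/9) = 1.03, 1.07, 1.12 for k = 1, 2, 3.

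**Adherence summary (illustration)**

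Now let k be the number of low compliers among all 18, with the others at an assumed 95%. The low compliers are at an assumed 50% or 70%. Mean = [(18 − k) × 95 + k × low]/18.

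| k | Mean, all 18 (low = 50%) | Mean, all 18 (low = 70%) | Mean, low compliers omitted | Share at ≥80%, all 18 (exact 95% CI) | Share, omitted (lower limit) |
|---|---|---|---|---|---|
| 1 | 92.5% | 93.6% | 95% | 17/18 = 94% (73–100) | 100% (80.5%) |
| 2 | 90.0% | 92.2% | 95% | 16/18 = 89% (65–99) | 100% (79.4%) |
| 3 | 87.5% | 90.8% | 95% | 15/18 = 83% (59–96) | 100% (78.2%) |

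With k = 0, nothing changes in any of these calculations.

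**The case against.** Much of the case on the other side stands.

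- **The rules are discretionary.** Re-education comes first, only repeated low compliance leads to a discussion, and the PI may decide that the assessments go ahead. This stands, but no criteria guide either choice, so discretion alone does not protect the outcome data.
- **Intention-to-treat is not formally contradicted.** A reader might infer that withdrawn participants leave the Aim 1 analysis. No section says so, and multiple imputation allows everyone randomised to be analysed. What remains is that imputation from better-adherent participants may carry the selection forward.
- **Adherence need not be distorted.** A reader might infer that the adherence result will describe only those who stay. Compliance is recorded on weekly calls, so a withdrawn participant would already have low adherence on record, and the CONSORT diagram will report withdrawals and missed assessments with reasons. The gap is only that section 2.5.2 does not define the denominator. Adherence is also one feasibility output among several, not the single purpose of the pilot. The diagram, however, counts lost outcomes and cannot recover them.
- **It may not happen.** Section 2.3.6 reports that no participant in the earlier pilot came near the 80% level. This is the documents' only evidence on frequency. It is limited reassurance: section 1.4 calls those data incomplete and reports completion for ten healthy controls.
- **The direction is unknown.** A reader might infer that removal leaves the better responders. Participants with hypotension could equally be those who respond most to the drug.

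**Conclusion.** The concern holds in a limited form. The compliance and biopsy rules permit avoidable loss of RPE and peak VO2 at Visit 5, for reasons that may relate to tolerability and hence to arm. This weakens the intention-to-treat estimate, and the imputation plan as written may not restore it. The documents do not support saying that the rules contradict intention-to-treat, that withdrawn participants are excluded from the analysis, or that the adherence result is distorted; adherence would be biased only if withdrawn participants were left out or cut short in its summary.

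One lost participant is 1/9 = 11% of an arm. The overstatement factors of 1.13 to 1.50 rest on 1 to 3 low compliers in the nitrite arm with no effect, and on dropping them or imputing them as if they were like the rest. These are assumptions; the plan gives no rate of low compliance and no effect in low compliers. They also describe a simple mean in one arm, not the planned baseline-adjusted contrast. Whether withdrawal for refusal before the first dose also falls after randomisation cannot be settled, because the timing of randomisation relative to the first biopsy is not stated. The change is worth making because it is cheap and the visits are already scheduled.

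**What to change.** 1. In section 2.3.6, the Visit 4 biopsy text in section 2.2, and section 6.4.7(c)–(d), separate stopping study drug from leaving follow-up. Add a sentence such as: *Every randomised participant who has taken at least one dose is invited to all non-biopsy post assessments, regardless of compliance or refusal of the second biopsy, subject to consent and safety.* For dosed participants this replaces the case-by-case choice about post assessments.
2. In section 2.5.2, state that adherence is summarised over all randomised participants, including those who stop drug or withdraw.
3. Leave decisions on dosing, on stopping drug, and the safety withdrawals in section 6.4.7(a)–(b) as they are. The change concerns data collection only.

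The cost is wording in four places, with no visits beyond those already scheduled. The downside is that poorly adherent participants may slightly dilute the observed effect, which an intention-to-treat analysis already accepts.
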